7.7.2 Application Site Reactions

At Baseline Visit (Day 1) and End of Treatment visit (Day 29) subjects will be evaluated for signs and symptoms of application site reactions,

Number and percentage of subjects with each severity will be presented by visit, sign/symptom and treatment.

7.7.3 Vital Signs

Vital signs, including blood pressure, heart rate and body temperature will be recorded at screening; at pre-dose and 12 hours post-dose on Day 1; and at pre-dose and 12 post-dose

hours on Day 29. Overall interpretation (normal, abnormal not clinically significant or abnormal clinically significant) will also be recorded.

Vital sign measurements can be repeated. Repeats will be handled as follows. At the screening visit the latest repeat will be used for analysis. On Day 1 and Day 29 the latest repeat obtained prior to dosing will be used for analysis at the pre-dose time-point and the latest repeat obtained after dosing will be used for analysis at the 12-hour post-dose time-point.

Vital signs and their changes from baseline will be summarized descriptively by visit and treatment. Overall interpretation will also be summarized. All results will be listed.

7.7.4 Physical Examination

Physical examination will be performed at screening and Day 29 visit. The following body systems will be examined: General Appearance; Skin; HEENT; Heart; Lungs; Muscular-Skeletal; Lymph nodes; Neurological; Gastrointestinal; Genitourinary; Extremities as well as other if necessary. Each system will be classified as normal, abnormal not clinically significant or abnormal clinically significant.

Number and percentage of subjects with each classification will be presented by body system, visit and treatment. All results will be listed.

[figure not shown]
7.7.5 Exposure to Product

The subjects will be instructed to use the diary to document all doses taken. Dosing information will be summarized on the eCRF.

Compliance with scheduled application of the study drug will be determined as [Actual number of applications] / [Planned number of applications] * 100%, where

- Actual number of applications will be taken from the eCRF ("Total number of doses applied" field in the "Investigational Product Use Compliance" form)
- Planned number of applications is 29.

Number of missed doses will be calculated as follows. The number of doses missed in the dosing period (between the first and the last study drug application) will be taken directly from the eCRF.

Duration of exposure will be calculated as Date of last use of study medication – Date of first use of study medication + 1. Duration of exposure will be summarized descriptively by treatment group.

Compliance and duration of exposure will be summarized for the Safety and mITT populations.

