At screening a written Informed Consent Form (ICF) has to be signed by the subject and the eligibility criteria of the subject will be evaluated by clinical assessments.

Subjects should sign

ICF prior to start of any study procedures, complete washout, and

Confidential Page 12 of 102

return to the clinic to conduct the remainder of the screening procedures.

Study subject numbers will be assigned to study subjects sequentially in the order in which study subjects are enrolled into the study.

After the screening visit, each qualified subject will return to the clinic on Day 1 for confirmation of eligibility. Eligible subjects will be assigned to one of the three study treatment groups as per the computer-generated randomization schedule, and the assigned study medication will be dispensed by the study site staff. Since this is a double-blind study, neither the study team at the site nor the subjects will know the treatment the subject is assigned.

The subject will be instructed to apply a pea-size amount of the study treatment to cover the entire face (forehead, chin, nose, and each cheek [avoiding the eyes and lips]), once daily preferably, at the same time each day, up to and including the day before scheduled Visit 4 (Day 29±2).

On Day 1 visit and Day 29±2 visit, the subject will apply the assigned medication at the clinic under the supervision of an Independent Dispenser (unblinded to the treatment the subject is receiving).

From Day 2 up to and including the day before scheduled Visit 4 (Day 29), the subject will be asked to apply the assigned medication once daily preferably, at the same time each day, and complete the subject diary, handed over by the study site staff at Baseline visit.

The subject will note the date and time of application of the study medication, any AE experienced, and any concomitant medication taken or changes from the existing ones, in the subject diary from Visit 2 (Day 1) to Visit 4 (Day 29). A phone call will be made around Day 14 to follow up for any change in concomitant medications, and check on compliance of study medication usage.

Confidential Page 13 of 102

Schedule of Events

			'isit		
	Visit 1a	Visit 1b	Visit 2	Visit 3	Visit 4
Procedures	Screening	Screening	Day 1 (Baseline)	Day 14 (Telephone Follow-up) ^a	Day 29 (EoT)
Written informed consent	X				
Demographics (height, weight, body mass index (BMI), gender, race, ethnicity)	X				
Pregnancy test (Urine)	X	X	X		X
Medical and surgical history	Х	X			

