3 STUDY DESIGN

3.1 Design Overview

This is a multi-center, randomized, double-blind, parallel-group, three-arm, placebo-controlled, therapeutic equivalence study with clinical end-point. The study will compare the efficacy and safety of Test Product "Oxymetazoline hydrochloride Cream, 1%" (manufactured by Actavis Laboratories, Salt Lake City, UT) with that of an approved topical formulation RHOFADETM (Oxymetazoline hydrochloride Cream, 1%) marketed by Allergan, in healthy males and non-pregnant females diagnosed with moderate to severe persistent facial erythema of rosacea. Both the test and the reference formulations will also be compared to a placebo (vehicle) formulation to test for superiority.

Subjects with a confirmed diagnosis of moderate to severe persistent facial erythema of rosacea will be randomized to one of the three treatment groups as follows:

Test Group: Oxymetazoline hydrochloride Cream, 1%, to be applied once daily preferably, and at the same time each day, for 29 days.

Reference Group: RHOFADETM (Oxymetazoline hydrochloride Cream, 1%), to be applied once daily preferably, and at the same time each day, for 29 days.

Placebo Group: Vehicle Cream, to be applied once daily preferably, and at the same time each day, for 29 days.

Planned sample size

Methodology

Confidential Page 29 of 102

The study subject will receive treatment for approximately 29 days from the Baseline visit to the End of Treatment (EoT) visit. There will be 4 study visits, 3 to the study site and 1 telephone follow-up: Screening visit (Visit 1), Baseline (Day 1 visit (Visit 2), Telephone Follow-up (Day 14 visit (Visit 3), and EoT (Day 29 visit (Visit 4).

At screening, a written Informed Consent Form (ICF) has to be signed by the subject and the eligibility criteria of the subject will be evaluated by clinical assessments. If necessary, subjects will be allowed to conduct screening procedures on two separate days in order to allow for enough time to complete the adequate washout period required for medications, makeup use, etc. Subjects should sign ICF (prior to the start of any study procedures), complete washout, and return to the clinic to conduct the remainder of the screening procedures.

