7.6 Safety Assessment

Safety analyses will be performed on the safety population. No inferential analyses are planned.

The extent of exposure will be summarized using descriptive statistics. Subject exposure to the study medication will be characterized by study duration and treatment duration. Study duration will be defined as number of days from the date of first dosing to the date of EoT visit (Day 29); if the date of EoT visit is missing, the date of the last visit will be used (i.e., date of study visit minus date of first dosing plus 1). Treatment duration will be defined as number of days from the date of first dosing to last dose (i.e., date of last dose minus date of first dose plus 1). Study duration and treatment duration will be summarized using descriptive statistics by treatment group.

Adverse events will be coded using preferred terms and primary SOC from the current version of MedDRA. The AEs and SAEs are considered to be treatment-emergent if they have started or worsened after first application of any study drug up until the EoT visit. The incidence of TEAEs, treatment-emergent SAEs (TESAEs) and drug-related TEAEs and TESAEs will be summarized by treatment group in frequency tables. The maximum severity of a TEAE/TESAE experienced by a subject will be determined by the most severe rating recorded on the eCRF for the subject's given TEAE. TEAEs leading to study discontinuation and treatment-related TEAEs leading to study discontinuation will be summarized by preferred term within primary SOC. Individual subject listings will be generated for TEAEs and TESAEs, including subject age, sex, and race, sorted by primary SOC, preferred term, onset and stop date, onset day relative to the most recent dose, relationship, and severity.

Adverse events will also be collected both for the screening and baseline period (which will be referred to as pretreatment AEs). A listing of pretreatment AEs (including any SAEs) will be presented.

Incidence of concomitant medications will be summarized by treatment group. A listing by subject of all abnormal physical examination values will be provided. The vital signs (body temperature, systolic blood pressure, diastolic blood pressure and heart rate), will be reviewed by the Investigator or qualified delegate and will be summarized by descriptive statistics.

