9.4 Primary Source Documents

The Investigator must maintain primary source documents supporting significant data for each study subject's medical notes. These documents, which are considered "source data", should include documentation of:

- Demographic information
- Evidence supporting the diagnosis/ondition for which the study subject is being studied
- General information supporting the study subject's participation in the study
- General history and physical findings
- Hospitalization or Emergency Room records (if applicable)
- Each study visit by date, including any evaluations, relevant findings/notes by the Investigator(s) occurrence (or lack) of AEs and changes in medication usage, including the date the study drug commenced and completed.
- Any additional visits during the study
- Any relevant telephone conversations with the study subject regarding the study or possible AEs
- An original, signed ICF for study participation
- Subject's diary

The Investigator must also retain all study subject specific printouts/reports of tests/procedures performed as a requirement of the study. During monitoring visits, the monitor will need to validate data in the CRFs against these sources of data.

Confidential Page 73 of 102

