The subject will be instructed to apply a pea-size amount of the study treatment to cover the entire face (forehead, chin, nose, and each cheek [avoiding the eyes and lips]), once daily preferably, at the same time each day, up to and including the day before scheduled Visit 4 (Day 29 ± 2). . On Day 1 visit and Day 29±2 visit, the subject will apply the assigned medication at the clinic under the supervision of an Independent Dispenser (unblinded to the treatment the subject is receiving).). From Day 2 up to and including the day before scheduled Visit 4 (Day 29), the subject will be asked to self-apply the assigned medication once daily and complete the subject diary, handed over by the study site staff at Baseline visit. The subject will note the date and time of application of the study medication, any AE experienced, and any concomitant medication taken or changes from the existing ones, in the subject diary from Visit 2 (Day 1) to Visit 4 (Day 29). A phone call will be made around Day 14 to follow up for any change in concomitant medications, and check on compliance of study medication usage. 3.2 Sample Size

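### SAP 7.7.5 divides every subject's doses by 29, but the schedule calls for 27 to 31, so a fully adherent completer is scored between 93.1% and 106.9% compliant

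*SAP*

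**What the plan says.** SAP 7.7.5 (Exposure to Product) presents compliance as adherence to the scheduled applications. The numerator is the total number of doses applied, read from the eCRF. The denominator is a constant: "Planned number of applications is 29". The section states no cap on the numerator and does not link the denominator to the date of Visit 4. It also reports missed doses and duration of exposure, and it uses compliance only for summaries in the Safety and mITT populations.

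The schedule itself is not constant. SAP 3.1 has the subject dose daily "up to and including the day before scheduled Visit 4 (Day 29 ± 2" days, with supervised clinic doses on Day 1 and at Visit 4. The protocol synopsis (Study Design and Methodology) agrees: "up to and including the day before scheduled Visit 4 (Day 29±2". Protocol 3.1 gives the nominal regimen for each arm: "to be applied once daily preferably, and at the same time each day, for 29 days".

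Protocol 7.6 already contains a subject-specific length: "Study duration will be defined as number of days from the date of first dosing to the date of EoT visit (Day 29"), calculated as "date of study visit minus date of first dosing plus 1".

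**The concern.** A measure of compliance with the schedule should give 100% to a subject who followed the schedule. Here it does so only when Visit 4 falls exactly on Day 29. Attending earlier or later within the permitted window is not non-compliance, yet it moves the score down or up.

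Under the dosing rule in SAP 3.1 and the synopsis, the extra doses before a late visit can also offset missed ones, so a subject with real omissions can appear fully compliant.

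The section can therefore contradict itself. A perfectly adherent subject seen on Day 27 would show no missed doses and 93.1% compliance. A subject seen on Day 31 who missed two doses would show two missed doses and 100% compliance. What is at stake is the accuracy of the reported adherence figures.

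**Working it through.** **Inputs.** Denominator 29 and the formula: SAP 7.7.5. Visit 4 on Day 29 ± 2, daily home dosing to the day before it, clinic doses on Day 1 and at Visit 4: SAP 3.1 and the protocol synopsis.

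**The plan's own figure.** 1 clinic dose (Day 1) + 27 home doses (Days 2 to 28) + 1 clinic dose (Day 29) = 29. The constant is right for a visit on Day 29.

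**Scheduled doses for a visit on Day V.** 1 (Day 1) + (V − 2) home days + 1 (clinic) = V.

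**Score of a fully adherent completer.** V / 29 × 100 under SAP 7.7.5, and V / V × 100 with a subject-specific denominator. Because first dosing is Day 1, the visit date minus the first-dose date plus 1 equals V.

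| Visit 4 day | Scheduled doses | Against 29 | Error in doses | Against own schedule |
|---|---|---|---|---|
| 27 | 27 | 93.1% | −2 | 100% |
| 28 | 28 | 96.6% | −1 | 100% |
| 29 | 29 | 100% | 0 | 100% |
| 30 | 30 | 103.4% | +1 | 100% |
| 31 | 31 | 106.9% | +2 | 100% |

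**Missed doses hidden by a late visit.**
- Day 31, 2 missed: scored 29/29 = 100%; true value 29/31 = 93.5%.
- Day 30, 1 missed: scored 29/29 = 100%; true value 29/30 = 96.7%.

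**Sensitivity to the home-dosing wording.** Protocol 3.1, Protocol 6.2, the schedule footnotes and SAP 11.1 describe home dosing as running from Day 2 to Day 28. Taken literally, that gives 27, 28, 29, 29 and 29 scheduled doses, and scores of 93.1%, 96.6%, 100%, 100% and 100%. The understatement for early visits is the same under either wording. The overstatement for late visits arises only under the SAP 3.1 and synopsis rule.

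**Group level.** The documents give no distribution of visit days. For a fully adherent group under the SAP 3.1 rule, the mean is bounded by 93.1% (all on Day 27) and 106.9% (all on Day 31). If visits are assumed to be spread evenly over the five days, the mean is 29/29 = 100.0%, with an artificial standard deviation of √2/29 = 4.9 percentage points.

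**The case against.** The best defence is that 29 is the nominal course, prescribed repeatedly in the protocol, and that dividing by it gives a legitimate measure: the share of the planned course received. That stands as a description of the ratio. It does not fit the label in SAP 7.7.5, which is compliance with the scheduled applications, because the same SAP schedules 27 to 31.

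A second defence is that the information survives elsewhere. Missed doses come directly from the eCRF, Protocol 5.7 captures both missed and additional applications, and exposure is dated separately: "Duration of exposure will be calculated as Date of last use of study medication" minus the date of first use plus 1. This is true, and it lets a careful reader detect the discrepancy. It does not correct the percentage.

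A third is that no inference depends on the figure. That stands in full for the available text: the equivalence and superiority analyses in SAP 7.6.3 do not use compliance.

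Two stronger readings are tempting, and the documents do not support either.

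- A reader might infer that the distorted percentage decides who enters the per-protocol population. SAP 6.3 refers to section 7.5 for those exclusions, and that section is not in the available text. No compliance threshold can be attributed to it.
- A reader might infer from the Day 2 to Day 28 wording that subjects seen on Day 30 or 31 go one or two days without treatment before the primary assessment. The documents use Day 29 as the nominal label for Visit 4, so Day 28 reads naturally as the day before it. SAP 3.1 and the synopsis state the operative rule explicitly, and it leaves no undosed day.

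**Conclusion.** The point holds as a definition error of limited consequence. With Visit 4 allowed on Days 27 to 31, the fixed denominator is wrong by up to 2 doses either way, or 6.9 percentage points for a fully adherent completer. The early-visit error does not depend on how the home-dosing text is read. The late-visit error, and the masking of missed doses, rest on the SAP 3.1 and synopsis rule, which is the better reading.

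The size for a whole arm cannot be stated without the distribution of visit days; the even-spread figures are an assumption. Only the descriptive compliance summary is shown to be affected. No effect on per-protocol membership, equivalence or superiority is shown. The correction is worth making because a stated rule yields a wrong number and the remedy costs almost nothing.

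**What to change.** Amend SAP 7.7.5 only:

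- For completers, define planned applications as the date of Visit 4 minus the date of first dose plus 1, which is the study duration of Protocol 7.6. Every in-window visit day then gives 100% for full adherence.
- For early discontinuers, keep 29 and label the ratio as the share of the full planned course, presented separately from completer compliance. An Early Discontinuation Visit, which under Protocol 6.2 follows the Day 29 procedures, should not be treated as Visit 4 for this purpose.

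The cost is a few lines of SAP text and a small programming change. Both dates are already needed for study duration, and no visit or data field is added.

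As an optional editorial step, the home-dosing wording in SAP 11.1 can be changed now to run from Day 2 up to and including the day before Visit 4. The matching text in Protocol 3.1, Protocol 6.2 and the schedule footnotes can wait for the next amendment, since Protocol 9.7 requires sponsor and IRB approval before a revision is implemented and no harm has been shown that would justify a separate submission.

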7.7.6 Exposure to Concomitant Medication

Prior and concomitant medications and concomitant non-drug therapies will be assessed at baseline and at each subsequent study visit. The start and stop date of concomitant medication use during the study will be provided in the data set, in addition to the reason for the medication use.

Medication or non-drug therapy will be classified as prior, if the end date is known and is prior to the first use of the study medication. Medications and non-drug therapies that are ongoing or ended after the first use of the study medication will be classified as concomitant. If the end date of the medication or non-drug therapy is unknown, it will also be considered concomitant.

Concomitant medications will be summarized by ATC class (the highest available level) and preferred name for each treatment group as coded by the World Health Organization Drug (WHODRUG) dictionary March-2019 B3. Each subject will be counted only once for each applicable preferred name and ATC class. Concomitant medications will also be listed in a bysubject listing. Prior medications will be listed only.

8. CHANGES FROM PROTOCOL-SPECIFIED ANALYSES

There are no changes from the protocol-specified analyses.

9. LIST OF PLANNED TABLES, FIGURES, AND LISTINGS

See separate document with the table, figure and listing shells.

11. APPENDICES

11.1 Study visit Schedule

	Visit 1a	Visit 1b	Visit 2	Visit 3	Visit 4
Procedures	Screening	Screening	Day 1 (Baseline)	Day 14 (Telephone follow-up) ^a	Day 29 (EoT)
Written informed consent	X				
Demographics (height, weight, body mass index (BMI), gender, race, ethnicity)	X				
Pregnancy test (Urine)	X	X	X		X
Medical and surgical history	X	X			
Prior and concomitant medications and concurrent procedures	X	X	X	X	X
Vital signs measurements (blood pressure, heart rate, body temperature)	X	X	Pre-dose and 12 hrs		Pre-dose and 12 hrs
Clinician Erythema Assessment (CEA)	X	X	Pre-dose, 3, 6, 9, and 12 hrs (± 30 minutes at each timepoint)		Pre-dose, 3, 6, 9, and 12 hrs (± 30 minutes at each timepoint)
Subject Self-Assessment (SSA) for rosacea facial redness	X	X	Pre-dose, 3, 6, 9, and 12 hrs (± 30 minutes at each timepoint)		Pre-dose, 3, 6, 9, and 12 hrs (± 30 minutes at each timepoint)
Physical examination	X				X
Review of Inclusion/Exclusion	X	X	Pre-dose (confirm eligibility)		
Randomization			X		
Dispense study medication tube			X		
Dosing (Days 1-29) ^b			X		X
Adverse event monitoring ^c	X	X	X	X	X
Subject diary review			X		X
Confinement in study clinic			≥12 hrs in clinic		≥12 hrs in clinic
Collection of study medication tube					X

^a 14 days after the first dose of study drug, a phone call will be made to follow-up on any changes in concomitant medications and check on compliance of study medication usage.

^b Subject will apply study medication once daily preferably at the same time each day from Day 2 to Day 28 at home, as instructed.

^c Including monitoring of application site dermatitis, application site pruritus, application site erythema, and application site pain, scaling or burning at Visit 2 and Visit 4.

11.2 Code Fragments

Therapeutic equivalence analysis in the primary endpoint

```
proc freq data=<dataset>
    tables <treatment>*<success> / riskdiffc;
run;
```

Note: this analysis needs to be performed on a dataset containing test and reference treatment subjects only.

Superiority analysis in the primary endpoint

```
ods output ExactTests=ExactTests;
proc logistic data=<dataset>;
  class <treatment> / param=ref;
  model <success> = <treatment>;
  strata <pooled site>;
  exact <treatment>;
run;
```

Note: p-value from exact CMH test is found in ExactTests dataset, variable ExactPValue.

Reference for exact CMH test: http://support.sas.com/kb/32/711.html.

This analysis needs to be performed separately for test and reference treatments on a dataset containing only test and placebo or reference and placebo treatment subjects.

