- Visit Screening A: Demographics, vital signs, urine pregnancy test, physical examination, assessment of facial erythema using CEA scale (Investigator's assessment) and SSA scale (subject's assessment), AE monitoring, concomitant medications and concurrent procedures.
- **Visit Screening B:** Urine pregnancy test, assessment of facial erythema using CEA scale (Investigator's assessment) and SSA scale (subject's assessment), AE monitoring, concomitant medications and concurrent procedures.
- Visit Day 1 (Baseline): Vital signs, urine pregnancy test, assessment of facial erythema using CEA scale (Investigator's assessment) and SSA scale (subject's assessment), AE monitoring, concomitant medications and concurrent procedures.
- Visit Day 14 (Telephone Follow Up): Any changes in concomitant medications and concurrent procedures, and compliance with study medication usage.
- Visit Day 29 (End of Treatment): Vital signs, urine pregnancy test, assessment of facial erythema using CEA scale (Investigator's assessment) and SSA scale (subject's assessment), AE monitoring, concomitant medications and concurrent procedures.

Sample Size

Statistical Analysis

Three analysis populations will be used: Per protocol (PP) population, mITT population, and safety population.

Analysis of the primary endpoint

Analyses will be conducted with the PP population for equivalence determination, and analyses with the mITT population will be for supportive superiority purposes.

Confidential Page 16 of 102

Equivalence testing

Therapeutic equivalence will be concluded if the 90% confidence interval for the difference between test and reference products ($\pi T - \pi R$) of the treatment success rates at all timepoints 3, 6, 9, and 12 hours post-application on Day 29 falls within the acceptance range of [-0.20, +0.20] using PP population.

• Superiority testing

A two-sided exact Cochran-Mantel-Haenszel test, stratified by clinical site, will be applied to test the difference between treatment success rates at all timepoints 3, 6, 9, and 12 hours post-application on Day 29 of Test or Reference Product and Placebo. The sensitivity of the equivalence analysis (superiority of Test Product and Reference Product over Placebo) will be established if active treatment success rate is higher than and statistically significantly different from (p-value < 0.05) that of the Placebo group for each active treatment using the mITT population. No adjustment will be made for multiplicity.

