7.7.1 Analysis of primary endpoint

• Equivalence testing

Therapeutic equivalence will be concluded if 90% continuity-corrected confidence interval for the difference between test and reference products $(\pi T - \pi R)$ of the treatment success rates at all timepoints 3, 6, 9, and 12 hours post-application on Day 29 falls within the acceptance range of [-0.20, +0.20] using PP population.

Confidential Page 69 of 102

• Superiority testing

A frequency distribution of subjects with at least a 2-grade decrease (improvement) on CEA scores by time point on Day 1 and Day 29 and by treatment group will be tabulated. A two-sided exact Cochran-Mantel-Haenszel test, stratified by clinical site, will be applied to test the difference between treatment success rates at all post-application timepoints on Day 29 of Test or Reference Product and Placebo. The sensitivity of the equivalence analysis (superiority of Test Product and Reference Product over Placebo) will be established if active treatment success rate is higher than and statistically significantly different from (p-value < 0.05) that of the Placebo group for each active treatment, using the mITT population. No adjustment will be made for multiplicity.

Version No.: 3.0;

Detailed statistical methods will be explained in SAP.

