5. HYPOTHESES TESTING

Hypothesis of Equivalence

A two-sided, continuity-corrected 90% confidence intervals on the Test-vs-Reference difference for the proportion of subjects with treatment success at all timepoints (3, 6, 9 and 12 hours post-application on Day 29) will be constructed. Therapeutic equivalence will be

established if the 90% confidence interval for the difference is contained within the interval [-0.20, +0.20] for the PP population.

Hypothesis of Superiority

The null hypotheses to be tested are that there is no difference in the proportions of subjects with treatment success at all time-points (3, 6, 9 and 12 hours post-application on Day 29). The evaluation of superiority will be conducted separately for the Test treatment versus the Placebo treatment and for the Reference treatment versus the Placebo treatment. The analysis will be conducted using two-sided, $\alpha = 0.05$, exact CMH test stratified by study site.

Superiority will be established if the success proportion for each active treatment is greater than, and statistically different from, that of the Placebo for the mITT population.

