7. STATISTICAL METHODS OF ANALYSIS

7.1 General Principles

In general, all data will be listed by treatment group, subject and visit/time-point where appropriate. The summary tables will also be stratified by, or have columns corresponding to, treatment groups.

All subjects will be identified by their unique subject numbers. Data from the screen failures will not be included in tables, listings, or figures.

The total number of subjects in the study group (N) under the stated population will be displayed in the header of summary tables.

Data will be summarized using descriptive statistics for continuous variables. Unless otherwise specified, descriptive statistics will include number of subjects, mean, standard deviation (SD), minimum, median, and maximum. The minimum and maximum statistics will be presented to the same number of decimal places as the original data. The mean and median will be presented to one more decimal place than the original data. The standard deviation will be presented to two more decimal places than the original data. The number of missing observations will be presented only if non-zero.

In summary tables of categorical variables, counts, and percentages will be used. The count [n] indicates the actual number of subjects in a particular category, which should always be less than or equal to the total number of subjects in the respective study group with known (non-missing) category [M]. Percentage will be obtained by: % = n/M*100. Unless otherwise specified, all percentages will be expressed to one decimal place.

All statistical tests will be two-sided at a significance level of $\alpha = 0.05$, unless otherwise indicated. No adjustment will be made for multiplicity.

Unless otherwise specified below, baseline for an assessment will be defined as the last available assessment obtained prior to the first application of the study drug.

In by-visit summaries only scheduled visits/time-points will be presented. Unscheduled assessments will not be included in by-visits summaries, however, will be shown in listings and may be used in selecting the baseline, if applicable.

Relative days will be calculated relative to the date of the first dose of the study medication. Relative days will be calculated as follows only when the full assessment date is known (i.e., partial dates will have missing relative days).

For assessment on or after the day of the first dose of the study drug:

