7.6.3.1 Analysis of Therapeutic Equivalence of Test and Reference Treatments

Two-sided, continuity-corrected, 90% confidence intervals on the Test-vs-Reference difference for the proportion of subjects with treatment success at all timepoints on Day 29 will be constructed. Therapeutic equivalence will be established if the 90% confidence interval for the difference is contained within the interval [-0.20, +0.20] for the PP population.

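### The SAP's sample code for the primary equivalence interval sets no confidence level, so it would return 95% limits where the protocol and SAP require 90%

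*SAP*

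**What the plan says.** The written rule is consistent wherever it appears.

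- Protocol synopsis, Statistical Analysis: "Therapeutic equivalence will be concluded if the 90% confidence interval for the difference between test and reference products" falls within the margin.
- Protocol 7.7.1: "Therapeutic equivalence will be concluded if 90% continuity-corrected confidence interval for the difference between test and reference products", with the same margin.
- SAP 5: "A two-sided, continuity-corrected 90% confidence intervals on the Test-vs-Reference difference".
- SAP 7.6.3.1: "Two-sided, continuity-corrected, 90% confidence intervals on the Test-vs-Reference difference", with equivalence established if the "confidence interval for the difference is contained within the interval [-0.20, +0.20] for the PP population".

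SAP 11.2 gives the SAS code for this analysis. Its TABLES statement reads "tables <treatment>*<success> / riskdiffc" and then closes. The only accompanying note restricts the dataset to the Test and Reference arms. Neither the code nor the note states a confidence level.

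SAP 8 declares: "There are no changes from the protocol-specified analyses".

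**The concern.** `RISKDIFFC` implements the continuity correction but does not set the level. In PROC FREQ the level comes from `ALPHA=`, which defaults to 0.05. The documents do not state that default; it is general knowledge of the software, which protocol section 7 names as SAS 9.4 or higher. The code also lacks any equivalence sub-option, which would have produced 90% limits at the default alpha. As printed, then, it returns 95% limits for the interval that decides the primary objective. SAP 8 rules out reading this as a deliberate change.

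The SAP's general level would not alert a programmer. SAP 7.1 begins "All statistical tests will be two-sided at a significance level of" and sets 0.05, which matches the software default.

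If the code were copied uncorrected, a trial meeting its pre-specified 90% criterion could be reported as not equivalent. If this came to light only after unblinding, the correction could be taken for a post hoc choice, even though the text supports it.

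**Working it through.** **Level implied by text and by code**

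| | Two-sided alpha | Each one-sided test | z |
|---|---|---|---|
| Protocol and SAP text | 0.10 | 0.05 | 1.645 |
| SAP 11.2 code, default level | 0.05 | 0.025 | 1.960 |

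The code does not reproduce the stated 90% level. Its normal-quantile term is too wide by 1.960/1.645 = 1.192, about 19%, whatever the sample size.

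**Interval**

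With n per arm (SAP 3.3 gives 1:1:1 allocation):

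(pT − pR) ± [ z·√(pT(1−pT)/n + pR(1−pR)/n) + (1/n + 1/n)/2 ]

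The result passes if both limits lie within [-0.20, +0.20]. Sample size and planning rates are redacted, so every n and success rate below is an assumption.

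**Worked example: 38/100 against 30/100**

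- Difference = 0.08.
- Standard error = √(0.38·0.62/100 + 0.30·0.70/100) = √0.004456 = 0.0668.
- Continuity correction = 1/100 = 0.01.
- 90%: half-width = 1.645·0.0668 + 0.01 = 0.1198; limits -0.040 to 0.1998, **pass**.
- 95%: half-width = 1.960·0.0668 + 0.01 = 0.1408; limits -0.061 to 0.221, **fail**.

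**Second example: 57/150 against 42/150**

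- Difference = 0.10, standard error = 0.0540, correction = 1/150 = 0.0067.
- 90%: 0.005 to 0.195, **pass**.
- 95%: -0.012 to 0.212, **fail**.

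**Largest Test count that still passes, Reference at 30%**

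| Reference | 90% limits | 95% limits |
|---|---|---|
| 30/100 | 38 (excess 8 points) | 35 (excess 5 points) |
| 75/250 | 106 (excess 12.4 points) | 103 (excess 11.2 points) |

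**Probability of concluding equivalence** (exact enumeration over both binomials)

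| n per arm | True rates, Test vs Reference | 90% limits | 95% limits |
|---|---|---|---|
| 100 | 40% vs 40% | 72.4% | 57.4% |
| 100 | 15% vs 15% | 96.4% | 92.8% |
| 150 | 40% vs 40% | 92.8% | 86.0% |
| 150 | 15% vs 15% | 99.7% | 99.3% |
| 250 | 40% vs 40% | 99.6% | 98.8% |
| 150 | 45% vs 40% | 80.3% | 71.1% |
| 150 | 20% vs 15% | 94.8% | 90.5% |
| 250 | 45% vs 40% | 95.2% | 91.3% |
| 250 | 20% vs 15% | 99.6% | 99.0% |
| 150 | 40% vs 20% (at the margin) | 3.8% | 1.8% |

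The last row shows the direction: false equivalence becomes rarer, not more common.

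**The case against.** The strongest reply is that the analysis is fully specified in the text and only an illustrative appendix is incomplete. The code is headed as fragments and uses placeholders, so someone must write the real program and would work from SAP 5 and 7.6.3.1. As extracted, the PROC FREQ line even lacks a semicolon before TABLES, so the fragment would not run unaltered; that may be a loss in PDF conversion, and nothing here depends on it. SAP 7.1 allows for exceptions to 0.05, and the 90% interval is one. The table shells, which are a separate document, may state the level. The error is conservative and can be reversed by re-running at the stated level.

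On size, the larger losses assume success near 40%. The only Reference rates in the documents are 12% to 18% per time-point, in the prescribing information in Appendix II. At such rates with equal arms the loss is small: 99.9% to 99.8% at 150 per arm and 12%, and 99.3% to 98.3% at 150 per arm and 18%.

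Much of this stands. The pre-specified rule is not in doubt, the harm requires uncorrected copying, and the power loss may be negligible. The label rates are not a firm guide, however: they require success on both the clinician and subject scales at a single time-point, whereas this trial uses the clinician scale alone at all four, so the rate could be higher or lower.

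The mismatch itself remains. The placeholders cover dataset and variable names; the options are literal. The neighbouring superiority code names the exact output variable to read, so the appendix is meant to be used.

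**Conclusion.** The concern holds. The code and the text prescribe different intervals for the primary decision, and that does not depend on sample size. It rests on two facts in the documents (the 90% requirement and the absence of any level in the code) and one outside them (the PROC FREQ default of 95%).

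The practical size cannot be fixed while sample size and planning rates are redacted. Across the assumed scenarios with no true difference, the loss of power runs from 15 percentage points (72.4% − 57.4%, 100 per arm at 40%) to well under one point with larger arms and low success rates. With a true 5-point excess at 150 per arm it is 9.2 points (80.3% − 71.1%) at 45% vs 40%, and 4.3 points (94.8% − 90.5%) at 20% vs 15%. There is no risk of a false claim of equivalence. This should be fixed, but it does not undermine the design.

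**What to change.** In SAP 11.2, add `alpha=0.10` after `riskdiffc` on the TABLES statement. Add one sentence to the note saying that the printed 90% limits are the ones compared with -0.20 and +0.20. While editing, check that the PROC FREQ line ends with a semicolon in the source file.

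The cost is one option and one sentence in the SAP's code appendix. The decision rule is unchanged and no protocol amendment is needed.
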